#### 4.6.2. Benefit Assessment

For OAB patients with urinary incontinence who do not have benefit by pharmacotherapy such as anticholinergic, the remaining treatment options are surgical interventions, etc. GSK1358820 is a promising drug to bridge the gap in the treatment algorithm between pharmacotherapy and surgical interventions, and has already been widely used for the treatment of urinary incontinence due to NDO in the US, EU and other countries.

In overseas phase III studies conducted in NDO patients with urinary incontinence, who had not been adequately managed with anticholinergic therapy (Studies 191622-515 and 191622-516), Botox 200 U demonstrated improvement in NDO -related symptoms / parameters (such as frequency of urinary incontinence) compared to placebo. Improvement in these symptoms / parameters with GSK1358820 is also expected in Study 204948.

Although Study 204948 is a placebo-controlled study, all subjects may be treated with GSK1358820 since 200 U of GSK1358820 will be the treatment received if subjects satisfy the criteria for re-treatment regardless of the treatment group they were randomized to for treatment 1.

#### 4.6.3. Overall Benefit: Risk Conclusion

Given the assessments to mitigate the risk to subjects enrolled in this study, the known potential risk of GSK1358820 is justified by the benefits that will be obtained to subjects with NDO.

### 5. SELECTION OF STUDY POPULATION AND WITHDRAWAL CRITERIA

Specific information regarding warnings, precautions, contraindications, adverse events, and other pertinent information on the GSK investigational product that may impact subject eligibility is provided in the IB, product label, and other pertinent documents.

Deviations from inclusion and exclusion criteria are not allowed because they can potentially jeopardize the scientific integrity of the study, regulatory acceptability or subject safety. Therefore, adherence to the criteria as specified in the protocol is essential.

#### 5.1. Inclusion Criteria

A subject will be eligible for inclusion in this study only if all of the following criteria apply:

NOTE: Verification at Screening and reconfirmation at the initiation of Treatment phase 1 (Week 0) are required, unless otherwise specified.

AGE
1. Aged $\geq 20$ years at the time of signing the informed consent

TYPE OF SUBJECT AND DIAGNOSIS INCLUDING DISEASE SEVERITY
2. Patient has urinary incontinence as a result of neurogenic detrusor overactivity for a period of at least 3 months prior to screening as a result of spinal cord injury or multiple sclerosis, determined by documented patient history. In addition: 
 
• Spinal cord injury patients must have a stable neurological injury level at C5 or below occurring <math>\geq 6</math> months prior to screening.
 
• Multiple sclerosis patients must be clinically stable in the investigator's opinion, for <math>\geq</math>
 

3 months prior to screening and have an Expanded Disability Status Scale (EDSS) score <math>\leq 6.5</math>.

3. Patient has NDO for a period of at least 3 months prior to screening, determined by documented patient history
 
 
• The presence of an IDC must also be demonstrated during the urodynamic assessment during the screening period or Day 1 (prior to randomization).
 

4. Patient has not been adequately managed with one or more medications (i.e.: anticholinergics or beta-3 adrenergic receptor agonist) for treatment of urinary incontinence due to NDO . Not adequately managed is defined as:
 
 
• An inadequate response after at least a 4-week period of medication(s) for urinary incontinence due to NDO on an optimized dose(s)a, i.e., patient is still incontinent despite medication(s) for urinary incontinence due to NDO, or
 
• Limiting side effects (i.e.: condition that subject reduced dosage or discontinued the medication due to side effect) after at least a 2-week period of medication(s) for urinary incontinence due to NDO on an optimized dose(s)a
 

5. Patient has <math>\geq 6</math> episodes of urinary incontinence, with no more than one urgency incontinence-free day in the 3-day patient bladder diary completed during the screening phase


6. Patient currently uses clean intermittent catheterization (CIC) and/or temporary indwelling balloon catheter, or is willing to use clean intermittent catheterization (CIC) to empty the bladder (continuous indwelling catheter is not permitted). Patients currently on CIC should be willing to maintain a CIC schedule of at least 3 times per day throughout the study. Caregiver may perform CIC. Patients must not use temporary indwelling balloon catheter during the 3-day patient bladder diary collection period.
 
a: approved dose for the indication of OAB or neurogenic bladder (urinary frequency, urinary incontinence, etc) in Japan.

## WEIGHT

- |  |
|--|
| 7. Body weight $\geq 40$ kg at screening |
|--|

## SEX

- |   |
|---|
| 
8. Males or females :
 
 
• Male subjects with female partners of child bearing potential must comply with the following contraception requirements from the time of first dose of study medication until the study exit. 
 
1) Vasectomy with documentation of azoospermia.
 
2) Male condom plus partner use of one of the contraceptive options below: 
 
• Intrauterine device or intrauterine system that meets the SOP effectiveness criteria including a <math><1\%</math> rate of failure per year, as stated in the product label [Hatcher, 2007]
 
• Oral Contraceptive, either combined or progestogen alone [Hatcher, 2007]
 
 
 
 
 
 |
|---|

These allowed methods of contraception are only effective when used consistently, correctly and in accordance with the product label. The investigator is responsible for ensuring that subjects understand how to properly use these methods of contraception.

- Female subject : is eligible to participate if she is not pregnant (as confirmed by a negative urine or serum human chorionic gonadotrophin (hCG) test), not lactating, and at least one of the following conditions applies:
  - 1) Non-reproductive potential defined as:
    - Pre-menopausal females with one of the following:
      - Documented tubal ligation
      - Documented hysteroscopic tubal occlusion procedure with follow-up confirmation of bilateral tubal occlusion
      - Hysterectomy
      - Documented Bilateral Oophorectomy
    - Postmenopausal defined as 12 months of spontaneous amenorrhea. Females on hormone replacement therapy (HRT) and whose menopausal status is in doubt will be required to use one of the highly effective contraception methods if they wish to continue their HRT during the study. Otherwise, they must discontinue HRT to allow confirmation of post-menopausal status prior to study enrolment.
  - 2) Reproductive potential and agrees to follow one of the options listed below in the GSK Modified List of Highly Effective Methods for Avoiding Pregnancy in Females of Reproductive Potential (FRP) requirements from 30 days prior to the first dose of study medication and until the study exit.

**GSK Modified List of Highly Effective Methods for Avoiding Pregnancy in Females of Reproductive Potential (FRP)\***

This list does not apply to FRP with same sex partners, when this is their preferred and usual lifestyle or for subjects who are and will continue to be abstinent from penile-vaginal intercourse on a long term and persistent basis.

1. Intrauterine device or intrauterine system that meets the SOP effectiveness criteria including a <1% rate of failure per year, as stated in the product label [Hatcher, 2007]
2. Oral Contraceptive, either combined or progestogen alone [Hatcher, 2007]
3. Male partner sterilization with documentation of azoospermia prior to the female subject's entry into the study, and this male is the sole partner for that subject [Hatcher, 2007]

\*: Contraceptive methods approved in Japan are shown

These allowed methods of contraception are only effective when used consistently, correctly and in accordance with the product label. The investigator is responsible for ensuring that subjects understand how to properly use these methods of contraception.

**INFORMED CONSENT**

9. Patient has given signed informed consent, including compliance with the requirements and restrictions listed in the consent form and in this protocol (e.g., complete bladder diaries and questionnaires, is able to collect volume voided per void measurements over a 24-hour period, and attend all study visits in the opinion of the investigator(or subinvestigator)

## 5.2. Exclusion Criteria

A subject will not be eligible for inclusion in this study if any of the following criteria apply:

NOTE: Verification at Screening and reconfirmation at the initiation of Treatment phase 1 (Week 0) are required, unless otherwise specified.

CONCURRENT CONDITIONS/MEDICAL HISTORY (INCLUDES LIVER FUNCTION AND QTc INTERVAL)

--

- |  |
|--|
| 
1. Patient has a history or evidence of any diseases, functional abnormalities or bladder surgery, other than NDO, that may have affected bladder function including but not limited to:
 
 
1) Bladder stones (including bladder stone surgery) within 6 months prior to screening or confirmed occurrence of bladder stones at the screening phase
 
2) Surgery (including minimally invasive surgery) within 1 year of screening for stress incontinence or pelvic organ prolapse
 
3) Current use of an electrostimulation / neuromodulation device for treatment of urinary incontinence.
Note: Use of any implantable device is prohibited within 4 weeks prior to initiation of Screening phase and throughout the study period. Use of any external device is discontinued at least 7days prior to the start of the screening phase
 
4) Current use of a baclofen pump
 
5) History of interstitial cystitis, in the opinion of the investigator (or subinvestigator)
 
6) Past or current evidence of hematuria due to urological / renal pathology or uninvestigated hematuria b
 
7) Past or current history of bladder cancer or other urothelial malignancy, positive result of urine cytology or uninvestigated suspicious urine cytology results c at the Screening phase.
 
8) An active genital infection, other than genital warts, either concurrently or within 4 weeks prior to Screening
 
9) Male with previous or current diagnosis of prostate cancer or a prostate specific antigen (PSA) level of >10 ng/mL at Screening d
 
10) Evidence of urethral and/or bladder outlet obstruction, in the opinion of the investigator (or subinvestigator)
 
 
2. Patient has a serum creatinine level >2 times the upper limit of normal (ULN) at screening
 
3. ALT > 2xULN; and bilirubin > 1.5xULN (isolated bilirubin > 1.5xULN is acceptable if bilirubin is fractionated and direct bilirubin <35%) at screening
 
4. Patient has current active liver or biliary disease (with the exception of Gilbert's syndrome or asymptomatic gallstones or otherwise stable chronic liver disease per investigator assessment)
 
NOTES:
 
 
• Stable chronic liver disease should generally be defined by the absence of ascites, encephalopathy, coagulopathy, hypoalbuminaemia, oesophageal or gastric varices, or persistent jaundice, or cirrhosis
 
• Chronic stable hepatitis B and C (e.g., presence of hepatitis B surface antigen (HBsAg) or positive hepatitis C antibody (HCVAb) test result within 3 months prior to first dose of study treatment) are acceptable if subject otherwise meets entry criteria
 
 |
|--|

5. QTc > 450 msec or QTc > 480 msec in subjects with Bundle Branch Block from the result of ECG at screening
 
Notes:
 
 
• The QTc is the QT interval corrected for heart rate according to Bazett's formula (QTcB), Fridericia's formula (QTcF), and/or another method, machine-read or manually over-read
 
• The specific formula that will be used to determine eligibility and discontinuation for an individual subject should be determined prior to initiation of the study. In other words, several different formulae cannot be used to calculate the QTc for an individual subject and then the lowest QTc value used to include or discontinue the subject from the trial
 
 
6. Patient has hemophilia or other clotting factor deficiencies or disorders that cause bleeding diathesis
 
7. Patient has aspiration pneumonia, aspiration pneumonitis or acute respiratory failure within 12 months prior to Screening.
 
8. Patient currently requires or may require use of supplemental oxygen therapy and/or ventilatory support
 
b: Patients with investigated hematuria may enter the study if urological / renal pathology has been ruled out to the satisfaction by the investigator (or subinvestigator)
 
c: Suspicious urine cytology abnormalities required that bladder cancer or other urothelial malignancy has been ruled out to the satisfaction of the investigator according to local site practice
 
d: Patients with a PSA level of <math>\geq 4</math> ng/mL but <math>\leq 10</math> ng/mL must have prostate cancer ruled out to the satisfaction of the investigator (or subinvestigator) according to local site practice

---


CONCOMITANT MEDICATIONS
 
9. Patient change or initiate or discontinue anticholinergic, beta-3 adrenergic receptor agonist or any other medications or therapies to treat urinary incontinence due to NDO, within 6 days prior to the start of the screening phase
 
10. Patient has been treated with any intravesical pharmacologic agent for urinary incontinence due to NDO during following period:
 
 
• Capsaicin or resiniferatoxin: within 12 months prior to initiation of Treatment phase 1 (Week 0)
 
• Anticholinergic within 4 weeks prior to start of screening
 
 
11. Patient has previous or current use of botulinum toxin therapy of any serotype for the treatment of any urological condition
 
12. Patient has previous use within 12 weeks prior to initiation of Treatment phase 1 (Week 0) or current use of botulinum toxin therapy of any serotype for any non-urological condition or beauty care
 
13. Patient has been immunized for botulinum toxin of any serotype
 
14. Patient cannot withhold any antiplatelet or anticoagulant therapy or medications with

---

- anticoagulative effects for 3 dayse prior to initiation of Treatment phase 1 (Week 0)
15. Patient without a UTI as determined from the urinalysis or urine culture and/or investigator opinion, has not initiated prophylactic antibiotic medication 1 to 3 days prior to the initiation of Treatment phase 1 (Week 0). Patient with a UTI as determined from the urinalysis or urine culture and/or investigator opinion, has not initiated antibiotic medication at least 5 days prior to the initiation of Treatment phase 1 (Week 0)
  16. Patient is symptomatic for UTI on day of treatment
- e: Some medications may need to be withheld for > 3 days, per clinical judgment of the investigator (or subinvestigator)

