#### DIAGNOSTIC ASSESSMENTS AND OTHER CRITERIA

20. Patient has a post void residual volume above 200 mLf for patients who micturate or have a mixed catheterization/spontaneous micturition pattern.
21. Patient has a 24-hour total volume of urine voided >3000 mL of urine collected over 24 consecutive hours during the 3-day bladder diary collection period in the Screening phase
22. Patient is currently participating in or has previously participated in another therapeutic study within 30 days prior to the start of the Screening phase
23. Patient has any condition or situation which, in the investigator's (or subinvestigator's) opinion, puts the patient at significant risk, may confound the study results, or may interfere significantly with the patient's participation in the study

f: The PVR measurement can be repeated once; the patient is to be excluded if the repeated measure is above 200 mL

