**Phase III-IV Liver Chemistry Increased Monitoring Algorithm with Continued Therapy for ALT ≥3xULN but <8xULN**

Liver Safety Required Actions and Follow up Assessments Section can be found in Appendix 12.2.

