7.1. Time and Events Table

**Table 1 Time and Events Table (Screening to Treatment phase 1)**

	Screening	Treatment phase 1										
	All subjects					If subject was not re-treated					Withdrawal	
Week (After 1st treatment)	Within 28 days	0	2	6	12	18 a (verification by tel.)	24	30 a (verification by tel.)	36	42 (verification by tel.)		48 (Study exit)
Window			± 3 d	± 7 d	± 7 d	± 7 d	± 7 d	± 7 d	± 7 d	± 7 d	± 7 d	
Patient characteristics etc.												
Informed consent	X											
Medical history / demographics	X	X b										
Inclusion / exclusion criteria	X	X b										
Neutralizing antibody	X m										X	X
Efficacy												
Urodynamic assessment	X c			X	X							
Check of bladder diary d		X b	X	X	X	X	X	X	X	X	X	X
KHQ		X b		X	X						X	X
TBS			X	X	X		X		X		X	X
Safety												
Adverse events e		X	X	X	X	X	X	X	X	X	X	X
Physical exam	X										X	X
Height, Weight	X										X f	X f
Vital signs	X	X b	X	X	X		X		X		X	X
ECG	X				X						X	X
Clinical laboratory (hematology and blood chemistry)	X				X						X	X
HBsAg · HCVAb (for subjects who receive or plan to receive immunosuppressants)	X											
Urinalysis (dipstick)	X	X b	X	X	X		X		X		X	X
Urinalysis (clinical laboratory) / Urine culture / sensitivity g	X	X b	X	X	X		X		X		X	X
PVR	X c		X	X	X		X		X		X	X
Ultrasound (kidney / bladder)	X				X						X	X
Urine cytology	X											
PSA (Only male)	X											
Urinary pregnancy test (Only females of reproductive potential) h	X	X b	X	X	X		X		X		X	X

EDSS (Only MS patients)	X											
Investigational product												
Treatment of antibiotic 		X										
Treatment of investigational product		X										
Confirmation of qualification for re-treatment criteria j, k					X	X	X	X	X			
Concomitant meds / therapies	X 	X	X	X	X	X	X	X	X	X	X	X

d = day (s)

- (a) Patient can request re-treatment at any time via telephone since week 12 after 1st treatment. If the patient requests re-treatment via telephone, a qualification for re-treatment visit should be conducted within approximately 1-2 weeks of the patient request.
- (b) Performed prior to treatment.
- (c) May be performed during the screening period through Day 1 (prior to randomization) excluding diary data collection days

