### Phase III-IV liver chemistry stopping criteria and required follow up assessments

Liver Chemistry Stopping Criteria - Liver Stopping Event	
ALT-absolute	ALT $\geq$ 8xULN
ALT Increase	ALT $\geq$ 5xULN but <8xULN persists for $\geq$ 2 weeks ALT $\geq$ 3xULN but <5xULN persists for $\geq$ 4 weeks
Bilirubin	ALT $\geq$ 3xULN and bilirubin $\geq$ 2xULN (>35% direct bilirubin)
INR^2	ALT $\geq$ 3xULN and INR>1.5, if INR measured
Cannot Monitor	ALT $\geq$ 5xULN but <8xULN and cannot be monitored weekly for $\geq$ 2 weeks ALT $\geq$ 3xULN but <5xULN and cannot be monitored weekly for $\geq$ 4 weeks
Symptomatic	ALT $\geq$ 3xULN associated with symptoms (new or worsening) believed to be related to liver injury or hypersensitivity
Required Actions and Follow up Assessments following ANY Liver Stopping Event	
Actions	Follow Up Assessments

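### Exclusion criterion 3 joins its ALT and bilirubin limits with 'and', so read literally it lets through isolated ALT elevation at any level

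*Protocol*

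**What the plan says.** Protocol section 5.2 opens with the rule for the whole list: "A subject will not be eligible for inclusion in this study if any of the following criteria apply". Criterion 3 is one item in that list. It names ALT above 2xULN and bilirubin above 1.5xULN, both at screening, joined as "2xULN; and bilirubin". A bracket then accepts isolated bilirubin above 1.5xULN if it has been fractionated and the direct part is below 35%.

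Two other criteria bear on the liver or on general risk:

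- Criterion 4 excludes active liver or biliary disease but spares several conditions, among them "or otherwise stable chronic liver disease per investigator assessment". Its notes accept chronic stable hepatitis B and C if the other entry criteria are met.
- Criterion 23 excludes any condition that, in the investigator's "opinion, puts the patient at significant risk, may confound the study results".

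Neither gives an ALT or bilirubin figure. Section 5 adds: "Deviations from inclusion and exclusion criteria are not allowed".

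**The concern.** Any one numbered item excludes, so a connector inside an item decides how much that item covers. With 'and', criterion 3 applies only when both limits are exceeded. The exception for isolated bilirubin then serves no purpose, because isolated bilirubin would never have excluded anyone. The criterion contradicts itself, and no other section restates it with 'or'.

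A site could still adopt the joint reading. The combined bilirubin rule in Appendix 2 (section 12.2) is written as "3xULN and bilirubin" and there it does mean both. Criterion 5, by contrast, uses 'or' between its alternative QTc limits.

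At stake is the only numeric liver limit at entry. Isolated ALT elevation is plausible in a trial that admits stable chronic liver disease. Sites could also differ on whether such a subject is an eligibility deviation, and SAP section 4.1 provides for a listing of those deviations.

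**Working it through.** The protocol states no figure to reproduce. The check is a case table followed by the laboratory schedule.

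**Inputs**

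- ALT limit 2xULN, bilirubin limit 1.5xULN and direct fraction 35%: criterion 3.
- Any one criterion excludes: opening of section 5.2.
- Screening within 28 days before first treatment, and Week 12 with a window of ±7 days: Time and Events Table 1, section 7.1.
- On-study stopping and monitoring levels: Appendix 2.

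**Step 1. The two rules**

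- Literal: exclude if ALT > 2xULN AND bilirubin > 1.5xULN.
- Implied by the exception: exclude if ALT > 2xULN OR bilirubin > 1.5xULN, sparing isolated bilirubin (ALT not above its limit) with direct fraction < 35%.

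**Step 2. The abnormal patterns**

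| ALT | Bilirubin | Direct fraction | Literal | Implied |
|---|---|---|---|---|
| ≤ 2x | > 1.5x | < 35% | pass | pass |
| ≤ 2x | > 1.5x | ≥ 35% | **pass** | **exclude** |
| > 2x | ≤ 1.5x | not applicable | **pass** | **exclude** |
| > 2x | > 1.5x | < 35% | exclude | exclude |
| > 2x | > 1.5x | ≥ 35% | exclude | exclude |

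Three of the five pass under the literal rule and one under the implied rule. The two rows in bold differ. A sixth pattern, with both values within limits, passes under either rule.

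**Step 3. Time to the next scheduled chemistry**

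The row "Clinical laboratory (hematology and blood chemistry") in Table 1 has entries at screening, Week 12, study exit and withdrawal, and none at Week 0.

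- Shortest gap: 0 + (84 − 7) = 77 days.
- Longest gap: 28 + (84 + 7) = 119 days.

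**Step 4. Against the on-study rules**

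Appendix 2 applies after entry, so it does not conflict with criterion 3. It does show how high an admitted value could be. ALT at or above 8xULN is a stopping event on study, yet the same value at screening with normal bilirubin passes criterion 3 as written. Below that, the section 5.5.1 algorithm is titled for "Continued Therapy for ALT ≥3xULN but <8xULN". A single value in that range leads to monitoring only, unless persistence, symptoms, raised bilirubin, raised INR or inability to monitor applies.

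**The case against.** The strongest reply is that the criterion resolves its own ambiguity. A reader who gives every part of the sentence some work to do must treat the limits as separate, since otherwise the bracket is empty. The section 5 ban on deviations covers the bracket as much as the connector, so it does not force the joint reading. The Appendix 2 rule is a weak parallel: it has no semicolon and no exception, and its ALT-only triggers sit in separate rows.

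The 77 to 119 days covers scheduled draws only. The text below Table 3 in section 7.4.6 asks for clinically significant abnormal values to be repeated until they return to normal or baseline, although whether that reaches a screening value is arguable. If a site did treat the screening value under Appendix 2, weekly or earlier repeats would follow. The pattern count is also unweighted and says nothing about how many patients are involved. Finally, the risk table in section 4.6.1 names no hepatic risk, and the SAP's adverse events of special interest (section 11.6.4) include no hepatic category.

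All of this bears on weight, and it is why the point is minor. It does not correct the text. A reader has to override the connector to reach the intended rule, no other section supplies an ALT limit at entry, and criteria 4 and 23 rest on investigator judgement.

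**Conclusion.** The concern holds. As worded, criterion 3 admits two patterns that its own exception implies should be excluded: ALT above 2xULN with bilirubin within its limit, and isolated bilirubin above 1.5xULN with direct fraction of 35% or more.

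The conclusion rests on the literal reading of the connector and on taking 'isolated' to mean that ALT is not above its limit. The practical effect is probably small: many investigators will apply the intended rule, criteria 4 and 23 may catch gross cases, and few of the 30 planned subjects are likely to be involved, though the documents give no count. Sample size, power and the primary analysis are unaffected.

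**What to change.** In criterion 3, replace the semicolon and 'and' with a comma and 'or', leaving the bracketed exception as it is. The criterion would then exclude on either limit, sparing only isolated bilirubin with a direct fraction below 35%. Alternatively, split it into two numbered criteria, one for ALT and one for bilirubin with its exception.

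Appendix 2 needs no change. The cost is one word, or one extra criterion number with renumbering of those that follow. Sample size and the SAP analyses stay as they are.
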